3.10 Sample size

Providing VE estimates for each separate study is one of the objectives of this project. Therefore, the minimum sample size should be estimated for each study to obtain precise CVE/IVE estimates. The pooled analyses should not prevent study teams at the country level from including a large enough sample size to obtain exact estimates for each country-specific study.

• Each study site/country to specify the minimum sample size calculation.

Sample size estimation in VE estimation is different from sample size estimation in hypothesis testing. Rather than focusing on whether a VE estimation includes 0% or not, it is the precision of the estimate which is more important. For example, with a VE of 70%, a lower boundary confidence interval of 1% does not provide a very informative VE estimate, even if the confidence interval does not include 0%. It is more important to have a VE estimate that is precise around the point estimate of 70% (e.g. with a lower boundary of 50%). In fact, a low VE estimate, which can be the case in particular stratified analyses, needs a very large sample size to provide a VE estimate where the confidence interval does not include 0%. For example, if the true VE is 5–10%, then a study providing a lower boundary not including 0% would be unreasonably large.

The following sample size estimates focus on precision of the VE estimate (Table 5).

The odds ratio (OR) has confidence intervals that are symmetrical around the point estimate in the log scale. However, due to the properties of the OR, these are asymmetrical around the point estimate on the arithmetic scale. The length of the confidence interval of an odds ratio on the arithmetic scale will therefore always be shorter at the lower limit (which will never reach zero). When converted to VE (VE=1-OR), the length of the confidence interval will always be shorter at the upper limit. Hence, the focus is on the precision of the lower limit of the confidence interval, and for Table 6 below, a potential range of between 10 and 30% (or 0.1–0.3) has been selected for this limit. A case-to-control ratio of 1:1 is also assumed, including varying vaccine coverage among the source population between 30% and 90%, and varying VE (with the OR between 0.1 and 0.7).

Table 5. Sample size calculations

Lower CI boundary	Controls/ case	Detectable OR	Vaccine coverage in source population/co ntrols	Number of cases	Number of controls	IVE/CVE	CI
0.3	1	0.1	0.3	60	60	90	60–98

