- use of medications for chronic conditions (e.g. statins, for IVE);
- Other stratifications may be included.

Virus variant-specific outcomes will be used, if available and feasible at the time of analysis.

A sufficient sample size should be planned in order to ensure enough individuals in each stratum for a precise estimate. Effect modification will be assessed comparing the OR across the strata of the potential effect modifiers. Confounding will be assessed by comparing crude and adjusted OR for each potential confounder.

Multivariable analysis

A multivariable logistic regression analysis will be conducted to control for negative and positive confounding. Odds ratios and standard errors will be obtained. Variables will be tested for multicollinearity. Interactions will be tested using the likelihood ratio test or Wald's test and will be included in the model if significant at the 5% level. Factors other than statistical significance (prevalence of exposure, magnitude of OR) will also be used as criteria for inclusion of a variable or an interaction term. If possible, a variable for sex, age and onset time should always be included in the model.

Continuous variables

Continuous variables in the COVID-19/influenza datasets include age, time of onset of symptoms, and hospitalisations in the past 12 months. These variables can be coded as categories (e.g. age group, week of symptom onset, etc.) However, when coding continuous variables as categories, information may be lost, or introduce residual confounding and increase the standard error of the model. Tests will be carried out to see if these variables could be coded as a linear term, polynomial or a spline. In addition, a balance will be sought between simplicity of a model (so a non-expert can understand it), precision and a model that estimates the vaccine effect with the least bias.

Identifying heterogeneity, testing for heterogeneity

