Individual study data will be pooled into one dataset and analysed as a one-stage model with study site as a fixed effect. This could provide a large enough sample size to obtain (for example) an estimate of CVE/IVE early in the study/season with reasonable precision. However, the results of this analysis should be interpreted with caution as it assumes not only that the underlying true exposure effect is the same in all studies, but also that the association of all covariates with the outcome is the same in all studies.

Formal tests of interaction between study site and covariates will be carried out to determine if the effect of each covariate differs across studies, to test the assumptions of the one-stage pooled fixed effect analysis.

The significance of interaction terms are themselves influenced by sample size and should also be interpreted with caution. Particular care needs to be taken if heterogeneity is found between study sites when using a one-stage fixed effects approach (see above section). Reasons for heterogeneity need to be thoroughly investigated and the assumptions underlying the one-stage pooling approach need to be revisited.

Controlling for hospital effect

Primary analysis will be carried out using simple logistic regression to obtain the individual study estimates. However, there could be an effect of the hospital that is related both to the exposure (propensity to vaccinate) and the outcome (in terms of swabbing behaviour). To adjust for this cluster effect, a multi-level logistic regression with each hospital as a random effect will be carried out when using one-stage pooled analysis.

Multi-level logistic regression can also be carried out for each individual study with hospital as a random effect. The two-stage model as outlined above will then be used to obtain a summary CVE/IVE measure, using these estimates.

The same applies to stratified analyses. The point estimates and confidence intervals from the multi-level and simple logistic regression will be compared in a sensitivity analysis.

Two-stage pooled analysis approach

If adequate sample size by study is achieved to obtain an adjusted OR, then a two-stage approach to pooled analysis will be taken.

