 - considering those vaccinated <X days before onset of symptoms as unvaccinated (in the main analysis these records will be excluded);
 - including SARI patients testing positive for influenza/SARS-CoV-2 in the control group;
 - including SARI patients testing positive for influenza/SARS-CoV-2 in the case group;
 - including SARI patients whose influenza/COVID-19 vaccine status is unknown in the control group;
 - using, as a control group, only SARI patients testing positive for at least one non-influenza respiratory virus/non-coronavirus;
 - considering different restrictions according to swabbing delay (e.g. <14 days, <10 days, etc.);
 - considering the sensitivity and specificity of PCR;
 - based on assumptions of previous infections;
 - excluding participants who received antivirals ≤14 days prior to swabbing;
 - excluding all participants with lab-confirmed influenza/SARS-CoV-2 at any time after symptom onset, to reduce bias.
- This can then be repeated using RSV as a sham outcome (if multiplex results are available for any sites).
 There should be no association between COVID-19/influenza vaccination and RSV-positivity in the absence of confounding.

Time can be input as a variable in the model to assess whether it can be an effect modifier.

Minimum sample size

Sample sizes may be very small for some sub-analyses. Different criteria can be used to determine whether the sample size is large enough to obtain a valid measure of VE;

- there are at least 10–15 cases (or controls, whichever is smaller) in the sub-analysis for crude analyses and more for adjusted analyses (e.g. at least 10 for each parameter in the model);
- there are ≥5 records in each cell of the two-by-two table of case and vaccination status;
- the precision of the estimate does not span both -200% and 90% (uninformative).

With low sample size, approaches include collapsing categories, or modelling continuous variables in a different way (if applicable). Sensitivity analyses can be carried out using penalised logistic regression.

Use of propensity scores

To limit the number of co-variables to include in the multivariable model, **if sample size allows**, estimates will be built and adjusted based on propensity scores. Propensity scores can be defined as the conditional probability of receiving the vaccine given a number of observed co-variables.

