In propensity score matching, a propensity score for vaccination is calculated for cases and controls. Cases and controls are then matched by propensity score and all non-matched patients are discarded. Variables used to calculate the propensity score will include variables related to the vaccination and outcome. Care will be taken to avoid correlation and overmatching.

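### The propensity-score step in Annex 2 matches cases to controls instead of vaccinated to unvaccinated, and names no matched analysis: VE would shrink towards zero if the matched set went through ordinary logistic regression without the score

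*Protocol*

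**What the plan says.** The last part of Annex 2, on the use of propensity scores, gives the purpose: "To limit the number of co-variables to include in the multivariable model". Provided the sample is large enough, "estimates will be built and adjusted based on propensity scores". The score concerns exposure: "Propensity scores can be defined as the conditional probability of receiving the vaccine given a number of observed co-variables". The operational sentence follows: "Cases and controls are then matched by propensity score and all non-matched patients are discarded". One caution closes the paragraph: "Care will be taken to avoid correlation and overmatching".

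The paragraph names no regression model for the matched set. Elsewhere in Annex 2 the models are these:

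- Multivariable analysis: "A multivariable logistic regression analysis will be conducted to control for negative and positive confounding".
- Controlling for hospital effect: "Primary analysis will be carried out using simple logistic regression to obtain the individual study estimates". A multi-level version has hospital as a random effect.

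Conditional logistic regression, or any other matched-set analysis, is not mentioned. No matching ratio, caliper or expected case:control ratio is given for this step. The only ratio stated is in section 3.10, for sample size: "A case-to-control ratio of 1:1 is also assumed".

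**The concern.** A score for vaccination makes vaccinated and unvaccinated patients comparable when those two groups are matched, stratified or adjusted on it. Here the groups being matched are cases and controls. Controls are then selected to resemble the cases on how likely they were to be vaccinated, so vaccination coverage in the two groups is drawn together by design. In a case-control study such matching must be reflected in the analysis. If it is ignored, the OR moves towards 1 and VE towards zero, even when the matching variable is not a confounder.

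At stake is a propensity-score VE that sits below the regression VE for a purely technical reason. A reader could take the gap as evidence that the main model had left confounding uncontrolled. Because this is a core protocol meant to be reused across sites and countries, the procedure would be copied.

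The second problem is the discarding. One score term in the logistic model already reduces the covariate count, and it uses every patient.

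**Working it through.** The Protocol gives no figure for this step, so there is none to reproduce. The scenarios use the ranges of section 3.10 (OR 0.1 to 0.7, coverage 30% to 90%, one control per case). As a check that these are read correctly, take the Table 5 row with OR 0.4, coverage 0.5 and a lower limit 10 points below the estimate:

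- p1 = 0.4 × 0.5 / (0.5 + 0.4 × 0.5) = 0.2857
- n = 1.96² × [1/(0.2857 × 0.7143) + 1/(0.5 × 0.5)] / ln(0.5/0.4)² = 3.8415 × 8.9 / 0.04979 = 687 cases, as printed.

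**Mechanism, by hand.** Assume two equal control strata with coverage 30% and 70% (50% overall), a true OR of 0.5 in each, no other effect of stratum on outcome, and enough controls to match every case.

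- Relative number of cases per stratum: 0.5 × (0.7 + 0.5 × 0.3) = 0.425 and 0.5 × (0.3 + 0.5 × 0.7) = 0.325. The shares are 56.7% and 43.3%.
- Coverage in cases: (0.5 × 0.5 × 0.3 + 0.5 × 0.5 × 0.7) / 0.75 = 33.3%, odds 0.5.
- Unmatched controls: 50%, odds 1. The crude OR is 0.5 and VE is 50%, which is correct.
- Controls matched on the score, here equivalent to stratum: 0.567 × 0.3 + 0.433 × 0.7 = 47.3%, odds 0.899. The OR is 0.5 / 0.899 = 0.556 and VE is 44.4%.

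Matching has moved the controls towards the cases and cost 5.6 points with no confounding present. Within strata the OR is still 0.5, which is why an analysis that respects the matching recovers it.

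**Simulation.** One normal covariate drives vaccination and, in half the scenarios, the outcome (log-OR 0.3). Coverage is 50%, with one control per case. The score is estimated in cases and controls together. Matching is greedy, 1:1, without replacement, with a caliper of 0.2 SD of the logit score. The SD of the logit score, the confounder effect, the caliper and the matching ratio are assumptions; the Protocol gives none of them. VE in %:

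| SD of logit score | True 50: matched, unconditional, score omitted | True 70: same analysis |
|---|---|---|
| 0.5 | about 48 | about 68 |
| 1 | 44–46 | 62–64 |
| 1.5 | 39–40 | 57–59 |
| 2 | 35 | 52–53 |

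A repeat for true VE 50% gave 47%, 44% and 35% at SD 0.5, 1 and 2. The alternatives, over the same scenarios:

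- Conditional analysis of the same pairs: 50–52% and 69–72%.
- Unconditional model on the matched set with the score kept in: 49–52% and 68–71%.
- Score as covariate in all patients, no matching: 50–52% and 70–71%.

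**Patients discarded.** With 1:1 matching, r controls per case and every case matched, the share kept is 2/(1 + r): 67% at r = 2, 50% at r = 3, 40% at r = 4, 25% at r = 7. The simulation agrees. At r = 1 the caliper decides: 79–97% are kept across scenarios, typically about 92%.

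**The case against.** The best defence is that the bias needs three things together: case-control matching, no conditional analysis, and a final model without the score. The paragraph assigns no model to the matched set. Its statement that estimates are adjusted on the score can be read as keeping the score in, which removes the bias. A matched-set model could also be named in a statistical analysis plan that is not shown. The paragraph warns against overmatching, and this is a form of overmatching.

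Part of this stands. The bias is conditional and must be stated so. But the matching of cases to controls is written out as the procedure; it is not a gap left for later. The only models Annex 2 offers are unconditional, and a general caution does not change the instruction that precedes it.

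Two stronger readings are tempting, and the Protocol supports neither:

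- A reader might infer that most patients would be thrown away, or about half the information lost. That needs roughly four controls per case with 1:1 matching. The Protocol states no such ratio, and at its only stated ratio, one control per case, most patients are kept.
- A reader might infer that the main VE estimates are biased. They are not affected: the step applies only if sample size allows, and the primary analysis is logistic regression without matching.

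The size also depends on how well the covariates predict vaccination. With weak prediction the loss is only about 2 to 3 points.

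**Conclusion.** The point holds in conditional form. Annex 2 matches on outcome where a vaccination score calls for a comparison by exposure, and it names no analysis that would account for this. Under the unconditional logistic regression it does name, with the score omitted, a true VE of 50% is underestimated by about 2 to 3 points at a logit-score SD of 0.5, 4 to 6 at SD 1 and 15 at SD 2. For a true VE of 70% the loss reaches 17 to 18 points at SD 2. Section 3.10 plans for lower limits 10 to 30 points below the estimate, so the larger losses matter on the plan's own scale. The SD is an assumption. Enrolment at all ages and age-prioritised vaccination make a clearly predictive score plausible, but the Protocol gives no value.

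Discarding unmatched patients serves no stated purpose. Its cost ranges from about 8% of patients at one control per case to about 60% at four with 1:1 matching. Since the step is a conditional add-on, this should be corrected but does not threaten the primary result.

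**What to change.** Replace the matching sentence in Annex 2. State that the propensity score for vaccination is entered as a covariate, as a spline or in strata, in the logistic model, with all cases and controls kept. This meets the stated aim of fewer covariates directly.

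If matching is to be retained, choose one of two forms and say which:

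- match vaccinated to unvaccinated patients on the score; or
- keep the case-control matched sets and analyse them by conditional logistic regression.

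Either form should state the matching ratio and caliper, and the number discarded should be reported, because both still lose patients.

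The cost is the rewording of one paragraph. The covariate version is less analysis work than matching and needs no new data.

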Annex 3. Genetic characterisation in vaccine effectiveness studies

Virus selection

Objectives

- To describe the viruses included in ECDC's COVID-19 and influenza vaccine effectiveness (CVE/IVE) studies (overall, by site and by time period), in order to identify key SARS-CoV-2/influenza virus genotypic evolution that could affect vaccine effectiveness.
- To measure genetic variant-specific CVE and (sub)type-specific IVE among study sites.

To meet these objectives, it is important that the viruses sequenced are representative of the influenza/SARS-CoV-2 viruses from cases belonging to the VE study population. To achieve this, either all or a random selection of viruses are sequenced (among those that are technically feasible to sequence). In this way the selection will be independent of vaccination or clinical outcomes.

Study sites/country will select viruses from SARI patients included in the CVE/IVE studies testing positive for SARS-CoV-2/influenza. If feasible, before virus selection, study sites/countries should verify if the influenza/SARS-CoV-2 positive cases meet the criteria used to include cases in the CVE/IVE pooled analysis (e.g. target group for vaccination, vaccination status and date documented, delay symptom onset swabbing no more than 10 days, etc.).

Proportion of SARS-CoV-2/influenza viruses to characterise sampling fraction

Each study country has different resources, different incidence and a different proportion of genetic variants circulating.

Ideally, a study site will sequence all viruses for which sequencing is technically feasible. If this is not feasible, then the proportion sequenced (the sampling fraction) will be based on the study site resources and the epidemiological/virological situation. As a minimum, we suggest study sites/countries sequence 50% of viruses for which sequencing is technically feasible, to be reviewed during the course of the pandemic.

If study sites are sequencing a proportion of viruses (as opposed to all viruses), the sampling fraction can change over time, depending on resources. For example, during peak incidence only 50% of viruses could be sequenced and during periods of low incidence all viruses could be sequenced. When sequencing a proportion of viruses it is then important to adhere to the random selection process.

The proportions sampled over time should be documented in the 'Example of sampling fraction definition' Excel spreadsheet. An example appears in Figure A1.

Figure A1. Example of how to define sampling fractions over time using the Excel spreadsheet 'Example of sampling fraction definition.xlsx'

Time		First date of	Last date of	Sampling	Date used for definition of time	Comments
period		time period	time period	fraction used	unit (onset date, swab date, other)	
	1	01/01/2021	31/01/2021	1	Date of swab	All specimens were characterised among those technically feasible
	2	01/02/2021	30/04/2021	0.5	Date of swab	50% of specimens were characterised among those technically feasible

Each study country to

- > define the sampling fraction used for each time interval (if all viruses characterised, then indicate 100%);
- document the sampling fraction for each time interval in the 'Example of sampling fraction definition.xlsx' document;
- take the sampling fraction into account when measuring site-specific genetic variant-specific VE (if applicable).

Procedures for random selection of specimens to be characterised

If a study country is not genetically characterising all viruses, then the random selection proposed should be used to select the viruses included in the multi-centre study. This should be done independent of any routine virological surveillance.

As it is difficult to prospectively randomise viruses to sequence, study sites can use a list of viruses by a predefined period (e.g. each week or month) to use for randomisation.

At the end of each period defined for the selection of strains, study sites will select viruses using random selection (e.g. the Bernoulli sampling method). This method ensures that each strain has the same probability of being selected.

Each site to define who selects the strains to sequence (e.g. team of epidemiologists, team of virologists).

Steps to randomly select strains

Step 1: Sampling frame

- Create a list of all positive cases recruited for the period that study sites/country would like to sequence (week/month).
- Viruses already characterised by the National Reference Centre (or other laboratories) during that period will be part of the sampling frame to ensure representativity.
- Viruses with low viral load will be part of the sampling frame.
- If possible, sites/countries will exclude from the sampling frame the viruses from cases that could later be excluded from any pooled analysis (e.g. target group for vaccination, vaccination status and date documented, delay symptom onset swabbing no more than 10 days, etc.).

Step 2: Randomisation

- List order all positive cases (viruses) by swab date.
- Assign a random number to each virus: the Excel function =RAND() can be used (this may be different if using
 a different language version of Excel).
- Copy the random number column and paste as values (this is important, otherwise they will keep changing) and then sort the list of cases (viruses) by random number in the pasted column (e.g. in order of high to low).

The STATA syntax below can be used. The example is a selection of 50% of 88 cases (44 strains to characterise).

```
sort swabdate
set seed 500
gen naleat=runiform(),
sort naleat
gen select=0
replace select=1 if _n<=44
list IDnumber strain select if select==1, noobs separator (44)
```

where 500 is the number used to set the seed. You can select another number but it is recommended that the 'set seed' be used to be able to replicate the selection.

Step 3: Selection

Based on the proportion of viruses sites/countries would like to sequence for this period (e.g. 50% or 75%), select the number of cases/viruses needed: start from the first case in the list and continue selecting the following cases until reaching the desired number (e.g. if 88 cases have been recruited in the study and the sampling fraction is 0.5, the first 44 cases in the list will be selected).

Step 4: Replacement of viruses randomly selected, but not characterised

Viruses that cannot be sequenced should be replaced using the same variant (or subtype/lineage) sampling frame. The strains will be replaced by the next ones in the list. So, for example, if 44 viruses would have been chosen from the randomised list and two are not feasible to sequence, then the viruses in the 45th and 46th line can be selected to sequence. The reasons for not sequencing selected specimens should be documented (e.g. low viral loads) and all study sites should document their Ct threshold for sequencing (if applicable).

Step 5: Increase in proportion sequenced if needed

If during the pandemic, the study site decides to increase the proportion sequenced for a given time period, it should go back to the sampling frame for that time period and continue selecting the subsequent strains from the ordered original list.

Data collected

For the viruses characterised, study sites/countries should fill in an Excel spreadsheet as shown below, with at least the following information available (see Figure A2 for an example):

- Country:
- Patient's study ID number;
- GISAID sequence database accession number;
- Selected for characterisation? (Y/N);
- Reasons for not characterising:
- If possible: Ct value;
- If possible: Type of sample (primary specimen or isolate).

Figure A2. Example of information collected on viruses using an Excel spreadsheet

Country	ID number	Reasons for no characterisation (for those selected not characterised)	Ct value clinical specimen	GISAID Accesion ID	
Spain	2016128	Sequenced	20.48	EPI_ISL_691732	
Spain	2016451	No product due to low viral load	31.52	N/A	

Screenshot of Excel spreadsheet to collect information on proportions sequenced over time (sampling fraction):

Time period	First date of time period	Last date of time period	Sampling fraction used	Date used for definition of time unit (onset date, swab of	Comments
1					
2					
3					
4					
5					
6					
7					
8					
Example1	01/01/2021	31/01/2021	1	Date of swab	(this is only an example
Example2	01/02/2021	30/04/2021	0.2	Date of swab	(this is only an example

Figure A3. Example of sampling fraction definition

Screenshot of Excel spreadsheet to collect information on proportions sequenced over time (sampling fraction):

Country	ID number	Reasons for no characterisation (for those selected not characterised)	Ct value clinical specimen	GISAID Accesion ID
Spain	2016128	Sequenced	20.48	EPI_ISL_691732
Spain	2016451	No product due to low viral load	31.52	N/A

Example of genetic and antigenic analysis data

The minimum amount of data needed to obtain genetic data from GISAID (sequences of all viruses should be sent to GISAID's open access EpiCoV platform) is country, ECDC SARI VE study patient ID number and GISAID accession number. Additional information on Ct value and selection for characterisation and reasons for not characterising can also be collected (see Table A1 below).

Table A1. Example of a data collection form for genetic data

	Country	Study ID number	GISAID accession ID number	Selected for characterisation?	Reasons for not characterising?	Ct value	Type of sample (primary specimen or isolate)
Strain 1							
1							
Strain							
2							

Where only a random selection of viruses were sequenced, additional information on sampling fraction should be provided, to better understand how viruses were selected for sequencing over time. An example can be seen in Table A2 below.

Table A2. Example of document outlining how viruses were selected for sequencing over time

Period	First date	Last date	Sampling fraction	Date used for definition of	Comments	
	of period		Traction	time unit (onset date, swab date, other)		
1						
2						
Example1	01/10/2020	31/12/2020	1	Date of onset	For example: all specimens were characterised	
Example2	01/01/2021	15/02/2021	0.2	Date of onset	For example: 20% of all specimens were characterised	

